## 2.2.1 Clinical

### 2.2.1.1 Completed studies

Five clinical studies of bimekizumab have been completed: UP0008 in 39 subjects with mild to moderate plaque PSO, RA0124 in 30 healthy volunteers, PA0007 in 53 subjects with PsA, UP0031 in 12 healthy volunteers, and UP0042 in 48 healthy volunteers.

UP0008 was a Phase 1, single ascending dose study in adults with mild-to-moderate PSO affecting  $\leq 5\%$  BSA. In this blinded study, single doses of up to 640mg (approximately 8mg/kg in an 80kg adult) were evaluated without any safety concerns. A total of 26 subjects with PSO with less than 5% of body surface involvement were treated with a range of single iv doses from 8mg to 640mg. There were no clinically relevant safety findings identified at any dose and all doses were well tolerated. The pre-specified exploratory assessment of disease activity showed clinically relevant and statistically significant improvements at the higher doses studied.

RA0124 was a Phase 1, open-label, parallel-group, single-dose study in healthy subjects. The primary objective of this study was to determine the absolute bioavailability (BA) of single sc doses of bimekizumab (80mg and 160mg). The secondary objectives were to evaluate the dose proportionality of bimekizumab 80mg and 160mg sc, and to evaluate the safety and tolerability of these sc doses and 160mg given by iv infusion. In RA0124, the absolute BA was similar for the 2 doses tested (0.656 and 0.631 for the bimekizumab 80mg and 160mg sc doses, respectively). The pharmacokinetics (PK) of bimekizumab was linear in the tested dose range and the median half-life following sc administration was similar to that following iv administration (27.81 days and 28.25 days for bimekizumab 160mg sc and 160mg iv, respectively).

Bimekizumab has also been investigated in a Phase 1b, proof of concept, randomized, placebo controlled, multiple dose study (PA0007). The primary objective of PA0007 was to assess the safety and PK of multiple dose administration of iv bimekizumab in subjects with PsA. Four active doses and a placebo were tested. Drug was administered as a loading dose at Week 0, and 2 additional doses were administered at Week 3 and Week 6. In each treatment group, subjects received a total of 3 doses of bimekizumab, administered every 3 weeks as shown below:

- 80mg loading dose followed by 40mg at Weeks 3 and 6
- 160mg loading dose followed by 80mg at Weeks 3 and 6
- 240mg loading dose followed by 160mg at Weeks 3 and 6
- 560mg loading dose followed by 320mg at Weeks 3 and 6

The results of this study demonstrated that all doses of bimekizumab were well tolerated and there were no unexpected clinically relevant safety findings.

Infections (mostly nasopharyngitis) were the most commonly reported events in both the active treatment and the placebo group. None of the infections were considered serious or required treatment with antibiotics. Two subjects in the active treatment group experienced 1 local candida infection each (oropharyngitis and vulvovaginitis, respectively) that were nonserious and resolved with topical therapy. There was a potential reduction in mean neutrophil count in the active treatment group, although this drop was not clinically relevant and a clear relationship

with dose or time was not evident. Some increases in liver function tests were reported, but none had a convincing relationship to exposure to IMP. The exploratory analysis showed clinically relevant improvement in activity of PsA and in skin involvement in those subjects with concomitant active psoriatic lesions.

UP0031 was a Phase 1, open-label, parallel-group, randomized, single-dose study to evaluate the BA, PK, and tolerability of 2 different formulations of bimekizumab in healthy subjects. Subjects receiving Formulation A (histidine-based) were administered two 1mL injections of 80mg each of bimekizumab and subjects receiving Formulation B (acetate-based) were administered a single injection of bimekizumab 160mg given as a 1mL injection. Six subjects were randomized to each bimekizumab formulation. The geometric means for area under the curve (AUC) were similar between bimekizumab 2x80mg and 1x160mg groups and the relative BA for Formulation B vs Formulation A was 96.1% (95% confidence interval [CI]: 72.7%, 127.0%). Administration of the 2 formulations of bimekizumab used in this study identified no new safety issues. There were no treatment-emergent adverse events (TEAEs) leading to discontinuation, and no serious adverse events (SAEs) or fatalities were reported. The only preferred term (PT) experienced by more than 1 subject in either treatment group was injection site pain (5 subjects [83.3%] and 3 subjects [50%] in the 2x80mg and 1x160mg groups, respectively). The most frequently reported TEAE considered related to the IMP was injection site pain, experienced by 5 subjects (83.3%) and 3 subjects (50.0%) in the 2x80mg and 1x160mg groups, respectively. There were no clinically significant laboratory values reported in the study.

UP0042 was a randomized double-blind, placebo-controlled, single-dose, parallel-group study to evaluate the safety, tolerability, and pharmacokinetics of bimekizumab administered as subcutaneous injection to Japanese and Caucasian healthy subjects. This study demonstrated that the PK profiles following single administration of 80mg, 160mg, and 320mg with sc injection were dose proportional with a linear elimination in both Japanese and Caucasian subjects and that the PK profiles of Japanese and Caucasian subjects were considered to be generally similar. A single dose of bimekizumab (80mg, 160mg, or 320mg) administered as sc injection was generally well tolerated in healthy Japanese and Caucasian subjects and no major differences in safety findings were observed between Japanese and Caucasian subjects.

Additional information on completed studies is available in the Investigator's Brochure (IB).

### **2.2.1.2 Ongoing studies**

All ongoing studies at the time of Protocol Amendment #5.4 implementation are presented and described in the current version of the IB.

### **2.2.2 Nonclinical**

Parallel inhibition of IL-17A and IL-17F has been shown to be efficacious in a variety of animal models of inflammatory disease. Intravenously administered bimekizumab was well tolerated in repeat dose toxicology studies in Cynomolgus monkeys with a no adverse effect level of 200mg/kg/week. The findings of note in toxicity studies were diarrhea related to infectious enteritis (observed in the single dose study) and asymptomatic mild colonic ulceration in a proportion of animals (in the repeat dose study); this latter finding was not associated with hematology abnormalities. Data suggest that bimekizumab has induced primary lesions to the mucosa associated lymphoid tissue via a pharmacologically related mechanism. In a second repeat-dose study, none of the minor apoptosis/necrosis findings observed in gut associated

lymph nodes were revealed. In animals given the highest dose of bimekizumab in the study (20mg/kg/week), a slightly higher number of protozoa (*Balantidium coli*) was observed in the cecum and colon as compared to the control animals and low dose animals. Therefore, gut associated lymph node lesions observed in the first study are considered to be accidental and/or linked to exaggerated pharmacology and proliferation of *Balantidium coli* and are considered the consequence of a change in local mucosal immunity. To date, similar findings have not been seen in studies in humans.

Additional information on the nonclinical data for bimekizumab is available in the current version of the IB.

### **3 STUDY OBJECTIVES**

#### **3.1 Primary objective**

The primary objective of this study is to compare the efficacy of bimekizumab administered sc for 16 weeks versus secukinumab at achieving complete clearance (PASI100) in subjects with moderate to severe chronic plaque PSO.

#### **3.2 Secondary objectives**

The secondary objectives of the study are to:

- Evaluate the efficacy of bimekizumab compared with secukinumab after 4 weeks, 16 weeks, and 48 weeks of treatment.
- Assess TEAEs, SAEs, and TEAEs leading to withdrawal adjusted by duration of subject exposure to IMP.

#### **3.3 Other objectives**

The other objectives of the study are to demonstrate the effects of bimekizumab on the following aspects of the disease:

- Assess the efficacy of bimekizumab over time
- Assess the change of skin-related quality of life (QOL)
- Assess the change of general health-related QOL
- Assess the change in nail PSO over time in subjects with nail PSO at Baseline
- Assess the change in psoriatic scalp disease over time in subjects with scalp PSO at Baseline
- Assess the change in psoriatic palmoplantar disease over time in subjects with palmoplantar PSO at Baseline
- Assess the change in patient global assessment PSO score
- Assess the change in symptoms of PSO (itch, pain, and scaling) as reported by subjects
- Assess work productivity status
- Assess the safety and tolerability of bimekizumab
- Assess the PK of bimekizumab

- Assess the immunogenicity of bimekizumab
- Assess the maintenance of efficacy of bimekizumab dosing Q4W versus Q8W
- Assess the safety and efficacy of initiating bimekizumab therapy in subjects who received secukinumab in the double-blind Treatment Period

## **4 STUDY VARIABLES**

### **4.1 Primary efficacy variable**

The primary efficacy variable is the PASI100 response, defined as complete clearance from Baseline in the PASI score, at Week 16.

### **4.2 Secondary variables**

#### **4.2.1 Secondary efficacy variables**

The secondary efficacy variables are:

- PASI75 response at Week 4
- PASI90 response at Week 16
- PASI100 response at Week 48
- IGA response (0/1) (defined as Clear or Almost Clear with at least a 2-category improvement relative to Baseline) at Week 16

#### **4.2.2 Secondary safety variables**

The secondary safety variables are:

- TEAEs adjusted by duration of subject exposure to IMP
- SAEs adjusted by duration of subject exposure to IMP
- TEAEs leading to withdrawal adjusted by duration of subject exposure to study treatment

### **4.3 Other variables**

The other variables are listed below and will be evaluated according to the planned assessments (Table 5-1, Table 5-2, and Table 5-3).

#### **4.3.1 Other efficacy variables**

The other efficacy variables are listed below and will be evaluated according to the planned assessments (Table 5-1, Table 5-2, and Table 5-3). This excludes the time points for the primary and secondary variables specified above in Section 4.1 and Section 4.2.1, respectively.

The other efficacy variables are:

- PASI75, PASI90, and PASI100 response
- Time to PASI75, PASI90, and PASI100 response
- Absolute and percent change from Baseline in PASI
- Percentage of subjects with PASI  $\leq 1$ ,  $\leq 2$ ,  $\leq 3$ , and  $\leq 5$

- IGA response (Clear)
- IGA response (Clear or Almost Clear with at least 2 category improvement relative to Baseline)
- Shift from Baseline in IGA score
- Absolute and percent change from Baseline in the BSA affected by PSO
- Absolute and percent change from Baseline in the product of IGA and BSA (IGAxBSA)
- Change from Baseline in Dermatology Life Quality Index (DLQI)
- Percent of subjects achieving a DLQI total score of 0 or 1
- Percent of subjects achieving a minimal clinically important difference (improvement from Baseline of 4 or more) in the DLQI
- Change from Baseline in the Patient's Global Assessment of Disease Activity (PGADA) for the arthritis visual analog scale (VAS) in subjects with PsA at Baseline
- Change from Baseline in Patient Global Assessment of PSO score
- Change from Baseline in symptoms of PSO (itch, pain, and scaling)
- Change from Baseline in Modified Nail Psoriasis Severity Index (mNAPSI) score for subjects with nail PSO at Baseline
- Percent of subjects achieving mNAPSI75, mNAPSI90, and mNAPSI100 for subjects with nail PSO at Baseline
- Scalp-specific Investigator's Global Assessment (scalp IGA) response (Clear or Almost Clear with at least 2-category improvement relative to Baseline) for subjects with scalp PSO at Baseline
- Palmoplantar Investigator's Global Assessment (pp-IGA) response (Clear or Almost Clear with at least 2-category improvement relative to Baseline) for subjects with palmoplantar PSO at Baseline
- Responses to the European Quality-of-Life 5-Dimensions 3-Level (EQ-5D-3L) dimensions, absolute and changes from Baseline in EQ-5D-3L VAS scores
- Change from Baseline in Work Productivity and Activity Impairment Questionnaire-specific health problem (WPAI-SHP) V2.0 adapted to PSO scores
- Change from Baseline in the Psoriatic Arthritis Screening and Evaluation (PASE) questionnaire scores (function score, symptom score, and total score)
- Shift from Baseline in PASE score suggestive of PsA (<47 versus  $\geq 47$ )

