### 9.4 Scalp IGA

A static IGA for scalp PSO will be used to assess disease severity on the scalp.

All subjects will complete the scalp IGA at Baseline. Only subjects with scalp involvement at Baseline will complete the scalp IGA at the other visits specified in Table 5–1 and Table 5–2. Subjects with scalp involvement at Baseline are defined as those with a scalp IGA score >0 at Baseline.

Scalp lesions will be assessed in terms of clinical signs of redness, thickness, and scaliness using a 5-point scale (Table 9–3).

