**Table 9–3: Scalp IGA**

| Score | Short Descriptor | Detailed Descriptor   |
|-------|------------------|---|
| 0     | Clear            | Scalp has no signs of PSO; post-inflammatory hyperpigmentation may be present   |
| 1     | Almost clear     | Scalp has no thickening; normal to pink coloration; no to minimal focal scaling   |
| 2     | Mild             | Scalp has just detectable to mild thickening; pink to light red coloration; predominately fine scaling                                    |
| 3     | Moderate         | Scalp has clearly distinguishable to moderate thickening; dull to bright red, moderate scaling  |
| 4     | Severe           | Scalp has severe thickening with hard edges; bright to deep dark red coloration; severe/coarse scaling covering almost all or all lesions |

PSO=psoriasis; scalp IGA=scalp-specific Investigator’s Global Assessment

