### 9.6 pp-IGA

A static IGA for palmoplantar PSO will be used to assess palmoplantar disease severity.

All subjects will complete the pp-IGA at Baseline. Only subjects with palmoplantar involvement at Baseline will complete the pp-IGA at the other visits specified in [Table 5–1](#) and [Table 5–2](#). Subjects with palmoplantar involvement at Baseline are defined as those with a pp-IGA score >0 at Baseline.

Palmoplantar disease will be assessed in terms of clinical signs of redness, thickness, and scaliness using a 5-point scale ([Table 9–4](#)).

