**Table 9–4: pp-IGA**

| Score | Short Descriptor | Detailed Descriptor  |
|-------|------------------|--|
| 0     | Clear            | Palmoplantar areas have no signs of PSO; post-inflammatory hyperpigmentation may be present  |
| 1     | Almost clear     | Palmoplantar areas have no thickening; normal to pink coloration; no to minimal focal scaling  |
| 2     | Mild             | Palmoplantar areas have just detectable to mild thickening; pink to light red coloration; predominately fine scaling   |
| 3     | Moderate         | Palmoplantar areas have clearly distinguishable to moderate thickening; dull to bright red and clearly distinguishable coloration; moderate scaling                        |
| 4     | Severe           | Palmoplantar areas have severe thickening with hard edges; bright to deep dark red coloration; severe/coarse scaling covering almost all or all lesions; numerous fissures |

pp-IGA=palmoplantar Investigator’s Global Assessment; PSO=psoriasis

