In general, data will be summarized by visit through Week 48 in the double-blind Treatment Period and then by visit in the OLE Period and OLE2 Period separately. All summaries of data up to Week 16 will be based on the RS for the 2 randomized treatment groups (bimekizumab and secukinumab). For visits after Week 16 in the double-blind Treatment Period, by-visit summaries will be prepared for the following 3 groups of subjects:

1. Subjects in the MS summarized by the 3 maintenance treatment groups (bimekizumab 320mg Q4W, bimekizumab 320mg Q8W, and secukinumab). Note that while the MS is primarily defined for the evaluation of data after Week 16, these summary tables will include data at all visits (Baseline to Week 48) to provide a comprehensive summary of subjects by maintenance treatment group for the MS.
2. A subset of Group 1 above. Specifically, this will include only those subjects who are responders at Week 16 for the variable being summarized. This will provide an assessment of how efficacy is maintained among Week 16 responders.
3. Subjects in the RS summarized by the 2 randomized treatment groups (bimekizumab and secukinumab). Data from Baseline to Week 48 will be included in these tables. This provides an intent-to-treat analysis among all randomized subjects in the study through Week 48.

All efficacy variables in the double-blind Treatment Period will be summarized in the manner described for Group 1 and 3 above. Summaries for Groups 2 will be done only for a subset of efficacy variables, namely, PASI75/90/100, IGA Clear or Almost Clear, Scalp IGA Clear or Almost Clear, pp-IGA Clear or Almost Clear, mNAPSI75/90/100, and DLQI 0/1.

In the OLE Period, efficacy variables of interest generally will be summarized descriptively by the combined treatment regimen in the double-blind Treatment Period and re-randomized treatment in the OLE.

In general, efficacy variables will be summarized using descriptive statistics by treatment group and scheduled visit during the OLE Period based on Baseline at beginning of the study unless otherwise specified.

In the OLE2 Period, selected efficacy variables of interest will be summarized descriptively by OLE2 Period Treatment Group during the OLE2 Period.

Further details on the above analyses including analysis in the OLE Period and OLE2 Period will be provided in the SAP.

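### Scalp IGA and pp-IGA response requires a 2-category improvement in a population that includes Baseline score 1, where that improvement is impossible

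*Protocol*

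**What the plan says.** Section 4.3.1 (Other efficacy variables) defines scalp IGA "response (Clear or Almost Clear with at least 2-category improvement relative to Baseline) for subjects with scalp PSO at Baseline" and pp-IGA "response (Clear or Almost Clear with at least 2-category improvement relative to Baseline) for subjects with palmoplantar PSO at Baseline".

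The populations come from the assessment sections. Section 9.4 states: "Subjects with scalp involvement at Baseline are defined as those with a scalp IGA score >0 at Baseline". Section 9.6 states: "Subjects with palmoplantar involvement at Baseline are defined as those with a pp-IGA score >0 at Baseline". Both scales run from 0 (clear) to 4 (severe). Score 1 is the almost-clear category, described in Table 9–3 as "Scalp has no thickening; normal to pink coloration; no to minimal focal scaling" and in Table 9–4 as "Palmoplantar areas have no thickening; normal to pink coloration; no to minimal focal scaling".

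Section 14.3.2.2 names these variables among those to be summarised in Week 16 responders, with the label "Scalp IGA Clear or Almost Clear, pp-IGA Clear or Almost Clear". That label omits the 2-category condition.

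For whole-body disease, Section 4.3.1 lists both the composite IGA response and a separate response of score 0 alone. It lists no score-0 response for the scalp or for the palms and soles.

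**The concern.** The response rule and the population do not fit together. The rule asks for a fall of two categories, but the population admits subjects who have only one category below them. Such a subject can reach the best possible outcome and still be recorded as a failure.

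The whole-body IGA uses the same rule safely, because inclusion criterion 5 (Section 6.1) requires an IGA of at least 3. No entry floor exists for scalp IGA or pp-IGA. Because no score-0 response is listed for these two sites, no other listed response variable credits clearance in score-1 subjects.

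At stake is the meaning of the reported response rates. They would depend partly on how many subjects happened to start at 1, and so would not describe how often the treatment works at these sites.

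**Working it through.** **Inputs from the protocol.** Response: post-Baseline score f ≤ 1 and fall b − f ≥ 2, where b is the Baseline score (Section 4.3.1). Population: b > 0 (Sections 9.4 and 9.6). Scale: 0 to 4 (Tables 9–3 and 9–4). The protocol states no figure for these variables that could be reproduced.

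**Step 1. Which follow-up scores count as response?**

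| Baseline b | In population (b > 0)? | Responding scores f |
|---|---|---|
| 0 | no | none |
| 1 | yes | none |
| 2 | yes | 0 |
| 3 | yes | 0, 1 |
| 4 | yes | 0, 1 |

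Score 1 is the only Baseline value inside the population with no responding score.

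**Step 2. Ceiling.** Let s be the share of the population with b = 1. If every other subject responds, the rate is 1 − s. The protocol does not give s. Assuming 10%, 20% or 30%, the ceiling is 90%, 80% or 70%.

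**Step 3. Dilution.** Let p₁ and p₂ be the response rates in the two arms among subjects with b ≥ 2. With the same s in both arms, the reported rates are p₁(1 − s) and p₂(1 − s), and their difference is (p₁ − p₂)(1 − s). Taking p₁ = 80% and p₂ = 70%, which are assumptions for illustration only:

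| s (assumed) | Reported rates | Reported difference |
|---|---|---|
| 0% | 80% vs 70% | 10 points |
| 10% | 72% vs 63% | 9 points |
| 20% | 64% vs 56% | 8 points |
| 30% | 56% vs 49% | 7 points |

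**Step 4. Chance imbalance.** If s differs between groups by d and both have the same rate p among subjects with b ≥ 2, the reported difference moves by p × d. With p = 80% and d = 5 points (both assumed), that is 0.80 × 5 = 4 points. Randomisation gives this no preferred direction.

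**Step 5. After restriction to b ≥ 2.** By the table in Step 1, every included subject has at least one responding score. The ceiling is 100% and the factor 1 − s disappears.

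**The case against.** **The denominator is partly inferred.** Section 4.3.1 speaks of scalp and palmoplantar PSO, while Sections 9.4 and 9.6 define involvement, and do so next to the sentence on who is scored at later visits. Section 14.3.2.2 leaves further detail to the SAP, which is not at hand and could restrict the population. The wording gap is real but narrow. No other definition is given, and Section 9.5 uses both terms for the nails under the same above-zero rule. A later document may repair the rule, but the protocol states it as it stands.

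**Score-1 subjects are already almost clear.** Without the 2-category condition they would be responders before any treatment, and counting them as nonresponders is conservative in both arms. This explains why an improvement condition is needed. It does not justify keeping in the denominator subjects who cannot meet it.

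**The consequence is limited.** These are other efficacy variables, summarised by treatment and visit, with no between-group test stated for them. They lie outside the fixed sequence in Section 14.2. This objection stands in full.

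Three stronger inferences are tempting, and the documents do not support them:

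- *That the ceiling carries into the Week 16 responder subset.* Under the Section 4.3.1 definition a score-1 subject can never be a Week 16 responder. Everyone in that subset therefore started at 2 or more, and no ceiling applies. If the shorter label in Section 14.3.2.2 were taken literally, score-1 subjects would already hold a responding score at Baseline. That is a labelling inconsistency and a different matter.
- *That the DLQI item has the same fault.* For "Percent of subjects achieving a minimal clinically important difference (improvement from Baseline of 4 or more) in the DLQI" it is true that a Baseline score below 4 cannot fall by 4. But Section 4.3.1 attaches no population to that item and lists change from Baseline and a score of 0 or 1 beside it. The denominator there is an open choice.
- *That the rule biases the treatment comparison.* Both arms are scored alike and randomised, so an imbalance in s is noise without direction.

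**Conclusion.** The point holds for scalp IGA and pp-IGA response. As written, subjects with Baseline score 1 are in the denominator and can never be in the numerator. The attainable rate is 1 − s, and with equal s in the arms the between-arm difference is multiplied by 1 − s. This follows from the protocol's definitions alone, on the reading that scalp or palmoplantar PSO means a Baseline score above 0.

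The size is unknown because s is not given. Assumed shares of 10% to 30% give ceilings of 90% to 70% and remove 10% to 30% of a between-arm difference in relative terms. The effect is dilution plus undirected noise in descriptive summaries. The primary result, the secondary tests and the type I error rate are unaffected.

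**What to change.** 1. In Section 4.3.1, and correspondingly in the SAP, restrict scalp IGA response and pp-IGA response to subjects with a Baseline score of 2 or more on the scale concerned.
2. In the same section, add score 0 as a response for each scale, reported for all subjects with a Baseline score above 0, so that clearance from score 1 is counted.
3. In Section 14.3.2.2, make the labels match the definition in Section 4.3.1, including the 2-category condition.
4. Leave the above-zero rule in Sections 9.4 and 9.6 unchanged. It decides who is scored after Baseline. Raising it to 2 would stop follow-up scoring of score-1 subjects and make item 2 impossible.

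The cost is a few lines of text and slightly smaller denominators for the two composite responses. No additional data are needed.
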